4. TRIAL DESIGN

Table 1: Trial Design

A	Study design	This is a randomised, multi centre, Phase II, prospective open label clinical trial.
---	--------------	--

		
There are two arms:
 
Treatment arm: Patient to receive treatment with camostat tablets, 200mg four times daily (qds) for 14 days
 
Control arm (non-treatment): Patient to receive best supportive care.

B	Patient group	Patients with COVID-19 infection who are symptomatic
C	Sample size	Up to 100 patients will be entered into this trial. Up to 50 patients in each arm. Patients will be randomised 1:1 into each arm.
D	Study intervention	
Patients in the treatment arm will be asked to take camostat for 14 consecutive days and patients in the control arm will be asked to continue with best supportive care.
 
Both groups will be asked to take [REDACTED] A clinical research team member will call the patient daily during this period. On Days 7 and 14, patients will be visited at home by the clinical research team, for blood draws [REDACTED] [REDACTED] Patients will also be called weekly (Days 21 and 28) before the follow up period ends.
 
Patients who are in hospital for non COVID-19 related reasons, who test positive for COVID-19, may also be recruited. Phone calls / home visits will be conducted where possible within hospital face to face.

E	Study analysis	Statistical Analysis Plan (Version 1.0, dated 27Sep2021)

For full details of the trial design, background and rationale for the study, please refer to the current study protocol.

5. PATIENT POPULATION AND ENDPOINTS

Patients must fulfil all the inclusion/exclusion criteria to be eligible for entry to the trial. Refer to the study protocol for the complete list of inclusion and exclusion criteria.

All enrolled patients who receive at least one dose of camostat will be evaluable for safety.

In order to be evaluable for efficacy, treatment arm patients must receive camostat for a minimum of five days, and control arm patients must either complete up to Day 14 or come off trial at an earlier timepoint due to an endpoint (e.g. hospitalisation)

5.1 Patient Populations

The analysis sets are defined as follows:

Full Analysis Population (FAP):	All enrolled patients.
	Patients who are enrolled in error onto the trial (due to ineligibility/administrative error), prior to receiving study treatment, will be excluded from the FAP.
Safety Population:	All enrolled patients who received at least one dose of camostat (or complete Day 1 of the control arm). Safety data will be collected from the date of written consent.
Efficacy Population:	Treatment arm patients must receive camostat for a minimum of five days, and control arm patients must either complete up to Day 14 or come off trial at an earlier timepoint due to an endpoint (e.g. hospitalisation).
Pharmacokinetic Population:	All enrolled patients who received one dose of camostat (or complete Day 1 of the control arm) – PK sample required (optional).

All other populations will be the same definition as Efficacy Population as defined above.

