13 DATA ANALYSIS AND STATISTICAL CONSIDERATIONS

13.1 Description of statistical methods

All statistical aspects of the study will be fully documented in a comprehensive Statistical Analysis Plan authored by the study statistician and agreed by the independent Trial Steering Committee.

The primary outcome will be an exploration of camostat safety and toxicity, in terms of the number and severity of AEs and SAEs.

Descriptive statistics will be used to describe the demographics for each randomised group and overall. For categorical data, frequencies will be reported, and for continuous variables means and standard deviations, or for skewed data, medians and interquartile ranges will be reported.

Secondary outcomes will be reported in a similar way to the demographic data, with an estimate of the difference and standard error between the treatment groups for continuous or ordinal scale data. Medians and IQRs will be used where data are non-normally distributed. Absolute percentage difference and standard error will be reported for binary variables. Kaplan-Meier plots and life tables will be used to estimate median survival times

Subgroups will be explored where there are sufficient patients in each group. Data will be split by age (< 65 years vs ≥ 65 years), fall in lymphocyte ($<20\%$ fall vs $\geq 20\%$ fall), and neutrophil:lymphocyte ratio (<2.18 vs ≥ 2.18) for key explanatory variables.

No significance testing will be performed. Differences between treatment groups will be reported solely to inform future trials.

All enrolled patients who receive at least one dose of camostat in the treatment arm and complete Day 1 in the control arm will be evaluable for safety.

In order to be evaluable for efficacy, treatment arm patients must receive camostat for a minimum of five days, and control arm patients must either complete up to Day 14 or come off trial at an earlier timepoint due to an endpoint (e.g. hospitalisation).

Safety data will be collected from the date of written, or verbal, consent. Safety variables will be summarised by descriptive statistics.

Adverse events will be reported as tables of frequency of AEs by MedDRA system organ class and by worst severity grade observed. Tables should indicate related and unrelated events

Adverse events will be reported for each arm and presented as tables of frequency of AEs by MedDRA system organ class and by worst severity grade observed. Tables should indicate related and unrelated events.

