6.6 Safety

Descriptive statistics will be used for evaluation of safety. The incidence of AEs will be summarised and displayed in frequency tables using counts and percentages. Additional parameters including but not limited to [REDACTED], and laboratory results will also be considered when evaluating safety.

Deaths, serious adverse events (SAEs) and events resulting in trial discontinuation will be tabulated.

Additional safety analyses may be determined at any time, in order to most clearly enumerate rates of toxicities and to further define the safety profile of camostat.

- The safety population is composed by all patients that receive at least one dose of camostat / complete Day 1 of control arm. The safety patient population will be used for the general safety presentations.

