6.7 Adverse Events

For patients on the treatment arm Pre-treatment AE's will be defined as those where "Did this AE start prior to first dose of IMP?" is ticked. Treatment Emergent AE's will be defined as those where "Did this AE start prior to first dose of IMP?" is not ticked. For patients on the control arm pre-treatment AE's will be defined as those where the AE started prior to Day 1. Treatment emergent AE's will be defined as those where the AE started after and inclusive of Day 1.

Treatment related AE's are those where causality to IMP is considered to be Possible, Probable or Highly Probable.

COVID-19 related AE's will be defined as those where "Is this AE related to COVID-19" is ticked yes.

The frequency of AEs will be summarised overall and by treatment arm. A patient can be counted multiple times per row for the No. of Episodes but will only be counted once per row for the No. of Patients.

Table 5: Frequency of All Adverse Events

Safety population

MedDRA System Organ Class (SOC) MedDRA Preferred Term	No. of Episodes Reported	No. of Patients N=XX	No. of Patients in Treatment Arm N=XX	No. of Patients in Control Arm N=XX
All AE's	N	N (%)	N (%)	N (%)
BLOOD AND LYMPHATIC...				
Anemia				
CARDIAC DISORDERS				
Sinus tachycardia				
Etc				

There will be additional versions of the above table based on pre-treatment AE's, treatment emergent AE's, treatment emergent SAE's (any AE that is considered Serious), related treatment emergent AE's. COVID-19 related AE's.

Overview of treatment emergent adverse events (by treatment arm). An AE is considered to have led to withdrawal if an adverse event with "Did the AE cause the subject to be discontinued from the study?" is recorded as yes.

Table 6: Overview of Treatment Emergent Adverse Events (Inclusive and post Day 1)

Safety population

Patients with TEAEs	Overall No. of Patients N=XX	No. of Patients in Treatment arm N=XX	No. of Patients in Control arm N=XX
Patients with >=1 TEAE	N (%)	N (%)	N (%)
Patients with >= 1 TE SAE			
Patients with >= 1 COVID-19 related			
Patients with >= 1 Treatment related			
Patients with >= 1 AE leading to withdrawal			
Patients who died			

Treatment emergent adverse events leading to withdrawal of treatment will be listed by patient. Patients will be included if an adverse event has "Action taken" recorded as "Drug Withdrawn" or "Did the AE cause the subject to be discontinued from the study?" is recorded as yes.

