11.1 Populations

The efficacy population will only include patients from the camostat arm where they have completed 5 days of treatment and in the control arm where they have completed 14 days of treatment or reached an endpoint (eg hospitalisation). All primary and secondary analyses will be conducted with this population. An intention-to-treat analysis of the main secondary outcomes (COVID-19 related hospital admissions, supplementary oxygen-free days, ventilator-free days, time to worst point on the 9-point ordinal scale) will also be conducted, should the data allow.

Patients who agree to the taking of blood samples will be included in the analysis of the PK data. The mean and SD will be reported at each time point (Days 7 and 14), as will the mean changes. The data may be log (or other) transformed if not normally distributed. [REDACTED]

[REDACTED] Change will be
change from previous blood test.

The safety population will include all patients with at least one dose of treatment (camostat or control). Safety data will be collected from the date of written consent. Safety variables will be summarised by descriptive statistics.

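### Unequal entry to the safety population: one dose is enough on camostat, but a control must complete Day 1, and other sections define the set differently

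*SAP*

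**What the plan says.** The SAP document is a reporting analysis plan with the statistical analysis plan appended. They are cited here as RAP and SAP.

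Four places give the same two-part rule:
- RAP 5.1: "All enrolled patients who received at least one dose of camostat (or complete Day 1 of the control arm".
- Protocol 13.1: "All enrolled patients who receive at least one dose of camostat in the treatment arm and complete Day 1 in the control arm". SAP section 10 repeats this text.
- RAP 6.6: "The safety population is composed by all patients that receive at least one dose of camostat / complete Day 1 of control arm".

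Two places differ:
- RAP section 5: "All enrolled patients who receive at least one dose of camostat will be evaluable for safety". Controls are not mentioned.
- SAP 11.1: "The safety population will include all patients with at least one dose of treatment (camostat or control". The control is best supportive care, labelled non-treatment in RAP section 4, so there is no dose to receive. The same section also assigns all primary and secondary analyses to the efficacy population.

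On use, RAP 6.6 states: "The safety patient population will be used for the general safety presentations". RAP Tables 5, 6 and 7 are headed as safety-population tables, and Table 6 has a row for deaths. For controls, RAP 6.7 says: "Treatment emergent AE's will be defined as those where the AE started after and inclusive of Day 1".

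**The concern.** A camostat patient enters the set by an exposure event. A control enters by getting through a day, a condition that can be failed because of an outcome. The safety rule makes no exception for death or an endpoint. The efficacy rule in RAP 5.1, by contrast, keeps controls who come off early because of an endpoint.

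The plan therefore collects Day 1 events in controls (protocol 12.1.1 requires AE reporting in both arms) and classes them as treatment-emergent, yet can drop the patient through the population rule. SAP section 12 calls the comparison of adverse events and their severity between arms the primary outcome, so this set carries the main result. A lost control event makes camostat look relatively worse. That is not harmless in a trial meant to support a move to Phase III.

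The conflicting definitions are a separate problem. A programmer cannot build one safety flag from these six texts, whether or not any patient is lost on Day 1.

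**Working it through.** **Plan's own figure.** None bears on this point. The only precision figure is for the recruitment rate (protocol 13.2). It reproduces with 100/0.50 = 200 patients approached: SE = sqrt(0.5 × 0.5/200) = 3.5%, giving 43% to 57%. Nothing below depends on it.

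**Who is counted under the majority rule, read literally:**

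| Case | Camostat | Control |
|---|---|---|
| Dies or leaves before the first dose / before Day 1 | Excluded | Excluded |
| Dies or leaves on Day 1, before any dose | Excluded | Excluded |
| Dies or leaves on Day 1, after the first dose (camostat) or at the same hour (control) | Counted | Excluded |
| AE on Day 1, stays on trial | Counted if dosed | Counted |
| Admitted on Day 1, stays on trial | Counted if dosed | Not clear |

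The clear difference between arms is confined to the interval from first dose to the end of Day 1. None of the sections cited says what completing Day 1 means. RAP 6.10 links Day 1 to the first administration by way of example, which gives controls no anchor.

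**Size per patient lost.** Inputs: 50 controls (RAP section 4, the maximum per arm); x control patients with an event, of whom k are lost on Day 1 (both assumed). The displayed rate is (x − k)/(50 − k), against x/50.

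| x | True rate | k = 1 | k = 2 |
|---|---|---|---|
| 2 | 2/50 = 4.0% | 1/49 = 2.0% (−2.0 points) | 0/48 = 0.0% (−4.0) |
| 5 | 5/50 = 10.0% | 4/49 = 8.2% (−1.8) | 3/48 = 6.25% (−3.8) |
| 8 | 8/50 = 16.0% | 7/49 = 14.3% (−1.7) | 6/48 = 12.5% (−3.5) |

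A control who leaves without an event changes only the denominator and moves the rate slightly the other way: 5/49 = 10.2%.

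**How likely is a loss?** The documents give no Day 1 loss rate. With an assumed chance q per control, P(at least one of 50 lost) = 1 − (1 − q)^50:

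| q | Expected number lost (50q) | P(at least one) |
|---|---|---|
| 0.5% | 0.25 | 22% |
| 1% | 0.5 | 39% |
| 2% | 1.0 | 64% |
| 5% | 2.5 | 92% |

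If five event patients were spread evenly over 28 days, 5 × 1/28 = 0.18 would be expected on Day 1. The k = 1 example is therefore well above an even spread.

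**Mirror case.** One camostat event patient lost before the first dose shifts that arm by the same arithmetic (5/50 to 4/49) and would cancel one control loss in the difference.

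**The case against.** A reader might infer four stronger things. The documents do not support them.

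- *A control admitted on Day 1 is dropped.* Protocol 5.1, 5.3.5 and 12.5 keep admitted patients in follow-up and ask for protocol assessments to continue, so such a control could still complete Day 1. The efficacy rule does speak of coming off trial for hospitalisation, so the case is ambiguous, not settled. It matters because patients may be randomised in an emergency department (protocol 9.1.2).
- *Controls must be event-free on Day 1.* They need not be. A control with a Day 1 event who stays on trial is counted, and RAP 6.7 calls the event treatment-emergent.
- *The events vanish from every AE table.* The registry AE and mortality tables (RAP 7.3) and the AE listings (RAP 8.1) name no safety-population restriction, and RAP 6.1 requires patients excluded from any population to be detailed.
- *The bias runs one way only.* Camostat also has a gate after randomisation, the first dose, and tablets may arrive by courier (footnotes to the protocol's Table 1). Events before that dose are lost in that arm.

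It can also be said that no significance testing is planned (protocol 13.1) and that any under-count of control events works against camostat. Both are true, and they limit the consequence.

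What remains is the different entry condition, its undefined key term and the conflict between sections. Disclosure only partly answers this: RAP 6.1 points to section 4.1 although the populations are in 5.1, and RAP 8.1 plans an exclusion listing for the efficacy analysis only.

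**Conclusion.** The point holds in a limited form. Four places set an entry rule that, read literally, removes a control who dies or leaves on Day 1 from RAP Tables 5 to 7 and their further versions, while a camostat patient with the same event after a first dose stays in. Control events in that interval would be understated. Because camostat events before the first dose are lost as well, the net direction is not certain.

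The effect is small: about 2 percentage points on the control rate per event patient lost, assuming 50 controls and true rates of 4% to 16%. Whether any patient would be lost cannot be judged from the documents.

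The inconsistency needs no assumption. RAP section 5 leaves no controls in the set, SAP 11.1 requires a dose that the control arm does not have, and SAP 11.1 sends primary analyses to the efficacy population although the AE tables are headed with the safety population. The correction should be made because it is cheap and concerns the primary outcome.

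**What to change.** 1. Use one definition in protocol 13.1, RAP 5, 5.1 and 6.6, and SAP 10 and 11.1. Camostat arm: at least one dose. Control arm: all randomised controls still on trial at the start of Day 1, with no completion condition. Remove the reference to a dose of control.
2. Define Day 1 for controls so that it parallels the first-dose day on camostat.
3. State in SAP 11.1 that AE analyses use the safety population.
4. Add a supporting table of AEs and deaths for all randomised patients, counted from randomisation. This is needed because item 1 alone would leave a reverse gap: a camostat patient who dies on Day 1 before dosing would be out, and a control at the same hour would be in.
5. List safety-population exclusions by arm with reasons, and correct the cross-reference in RAP 6.1.

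The cost is one extra table and a wording amendment to the protocol and the RAP/SAP. Protocol 15.4 notes that an amendment may need ethics, HRA and MHRA review. No new data are needed, since AEs are already recorded in both arms from consent.

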6. DATA CONVENTIONS AND GENERAL ANALYSIS

6.1 Patient disposition

Patients excluded from any population (defined in Section 4.1) will be detailed.

The accrual and trial discontinuation details will be presented descriptively. This should include details of:

- Screening failure patients (screening failure information is available via the e-screening logs).
- Information on ineligible patients who were enrolled and/or received camosat (and control).
- Reasons for treatment discontinuation by number of doses received will be described by counts and percentages. Reasons for treatment discontinuation other than disease progression will be detailed and summarised separately (Section 5.1.2).

6.2 Baseline characteristics

Demographics and baseline characteristics will be summarised for all enrolled patients. Patients will be included to the randomised arm regardless of whether they received treatment or not.

Table 1: Baseline characteristics by treatment arm

Full Analysis Population.

	All	Treatment arm	Control arm
Patients			
Male Total			
Male \geq 65 year old			
Male < 65 years old			
Female Total			
Female \geq 65 year old			
Female < 65 years old			
Age (Years)			
Mean (SD)			
Median (IQR)			
Min			
Max			
BMI			
Mean (SD)			
Median (IQR)			
Min			
Max			
Ethnicity			
COVID-19 Vulnerability Level			
Low			
Moderate			
High			

Very High			
COVID-19 age			
Mean (SD)			
Median (IQR)			
Min			
Max			
Ethnicity			
Asian / Asian British - Indian			
Asian / Asian British - Pakistani			
White-English / Welsh / Scottish / Northern Irish / British			
Any other white background			

In case of pre-treatment characteristics with multiple measurements per patient before the start of treatment (laboratory assessments, vital signs), the baseline measurement will be considered the last value prior to or on the first day of treatment.

Other baseline assessments, including medical history, will be covered within the listings per patient..

6.3 Patient withdrawal / Completion

Reasons for patient withdrawal will be provided as the data is available and presented for each randomised treatment arm.

Table 2: Reasons for patient withdrawal / completion

Reason off study	No. of Patients (N=XX)	Patient Number (patients who withdrew only)	No. of patients in Treatment arm	No. of patients in Control arm
Completion of treatment / monitoring period	XX (%)		XX (%)	XX (%)
Recovered				
Adverse event/Serious adverse event				
Pregnancy				
Death				
Investigator withdrawal of subject				
Subject withdrawal of consent				
Subject withdrawal from treatment (treatment arm) / subject withdrawal (allows FU) (control arm)				
Protocol deviations				

Sponsor's decision to terminate the trial				
Other				
Lost to follow up				

Full Analysis Population

6.4 Protocol deviations

A protocol deviation is defined as any departure from what is described in the protocol of a clinical trial approved by an Independent Ethics Committee and Competent Authorities. Therefore, it applies to deviations related to patient inclusion and clinical procedures (e.g. assessments to be conducted or parameters to be determined), and also to other procedures described in the protocol that concern the Good Clinical Practice (GCP) guidelines or ethical issues (e.g. issues related to obtaining the patients' Informed Consent, data reporting, the responsibilities of the Investigator, etc.).

Protocol deviations are captured throughout the trial open phase on the Sponsor's central tracker and can be filtered by study and by deviation category or on the study specific PK/PD deviations tracker. Standard deviation categories have been defined by the Sponsor and are further defined by those which are deemed reportable (important deviations) in the Clinical Study Report (CSR). Those deviations which have been coded as CSR reportable will be summarised for all patients, according to the categories allocated at identification. Deviations are reviewed manually as per Sponsor SOPs.

A summary table with the number of patients with deviations will be presented per criterion. Deviations with no effects on the risk/benefit ratio of the clinical trial (such as minimal delays in assessments or visits) will be distinguished from those that might have an effect on this risk/benefit ratio.

The following are pre-defined protocol deviations with a direct bearing on the primary outcome and therefore will be reported in the CSR. A summary including but not necessarily restricted to the following categories will be presented:

- Ineligible patients as per protocol.
- Patient not withdrawn as per protocol.
- Excluded concomitant medication.
- Incorrect IMP dose or schedule

6.5 Treatment compliance

A list of all treatment compliance by patient will be produced for those patients on the treatment arm only.

Table 3: Treatment modifications and/or non-compliance (treatment arm only)

Patient number	Date of first dose	Date of treatment modification	Description of treatment modification/non-compliance	Comment

Full Analysis Population (Treatment arm only)

6.6 Safety

Descriptive statistics will be used for evaluation of safety. The incidence of AEs will be summarised and displayed in frequency tables using counts and percentages. Additional parameters including but not limited to [REDACTED], and laboratory results will also be considered when evaluating safety.

Deaths, serious adverse events (SAEs) and events resulting in trial discontinuation will be tabulated.

Additional safety analyses may be determined at any time, in order to most clearly enumerate rates of toxicities and to further define the safety profile of camostat.

- The safety population is composed by all patients that receive at least one dose of camostat / complete Day 1 of control arm. The safety patient population will be used for the general safety presentations.

